4.3 Bias

4.4 Blinding and Randomisation

To minimise bias, participants will be allocated to treatment group based on minimisation. Blinding is not possible in this open label study and hence the maintenance of breaking codes is not required.

Minimisation will be used to allocate participants to study group based on the following balancing factors measured at baseline: age at Visit 1 (<6 years, 6 years and above), time in target range (<55%, greater or equal to 55%) collected from blinded sensor data, and study site. Minimisation is a method of ensuring excellent balance between groups for known prognostic factors(20). The Minimpy program (MinimPy)(19) will be used to allocate participants. Allocation will be undertaken by the delegated persons at Perth Children's Hospital.

4.5 Device Tracking

Device serial numbers will be attributed to each study participant and recorded on an excel worksheet as well as REDCap when they are issued. At the conclusion of the study, devices will be returned and checked off against the excel worksheet.

4.6 Intervention/Product Description

The AHCL system comprises the Medtronic MiniMed™ 780G insulin pump containing the closed loop algorithm, a next generation glucose sensor and a glucose sensor transmitter. The algorithm is contained in the pump and receives sensor glucose data every 5 minutes, computing and adjusting "basal rate" insulin delivery based on the glucose levels. Automated correction doses will be delivered with high sensor glucose levels. Meals will still be announced, and an insulin bolus delivered according to the individualised patient's insulin carbohydrate ratio.

4.7 Product Accountability Procedures

The study investigators will be responsible for patient safety during the study. The participants on the AHCL system will be contacted on a regular basis to monitor progress and help troubleshoot the problems.

4.8 Trial Duration/Schedule

Feasibility Phase: For each participant, the study duration is 8 weeks.

RCT Phase: The trial is expected to take 24 months for recruitment, completion of study visits and data analysis. For each participant, the expected study duration is 3 months.

4.9 Trial Termination

Study participation is voluntary, and participants may withdraw at any time. The DSMB will report to the ethics committees and investigators if stopping the study is required.

In general, once a participant is randomised, he/she will remain in the study unless the investigator believes it is not safe for the participant to continue. However, the criteria below will be used to determine whether use of the AHCL should be discontinued for a participant.

1. Severe hypoglycaemia (seizure or coma or any episodes requiring glucagon).
2. Severe diabetic ketoacidosis (venous ph <7.2)
3. Non-compliance with the protocol or development of a new medical condition or need for chronic use of a medication which in the judgment of the investigator increases risk for the participant

If AHCL use is stopped according to the above criteria, but the participant is willing, they will remain in the study and will continue to make all of the scheduled visits and participate in all monitoring.

The primary analysis will be intention to treat. Since participants in the usual care arm are following their normal diabetes care regimen, there will be no change in their participation in the study if they experience one of the events that would trigger stopping.

Criteria for Suspending/Stopping Overall Study

The DSMB will provide guidance to the Lead Investigator as to whether the overall study should be stopped.

In case of a recurring system malfunction or participant safety issue observed with multiple participants, the overall study will be suspended while the problem is diagnosed. The study may resume if the underlying problem can be corrected by a protocol or system modification that will not invalidate the results obtained prior to suspension.

The primary safety outcome will be

Severe hypoglycaemia (coma, convulsion or any episodes requiring glucagon). A sequential monitoring approach described by Kramar and Bascoul-Mollevi (2009) will be taken to determine study cessation rules due to excess severe hypoglycaemia. As hypoglycaemia events are experienced during the study, the DSMB will be notified in real time. The maximum acceptable rate of severe hypoglycaemia as well as the approach taken with regard to 'alpha spend' to preserve the nominal alpha of 0.05 will be determined in conjunction with the DSMB prior to the commencement of the study.

An instance of severe DKA from Automode use (algorithm-related) in the AHCL group will result in temporarily stopping additional enrolment of participants until DSMB review of the data to determine whether the event was triggered by the system or not and whether it is safe to proceed. An emergency meeting of the DSMB will be convened within 7 days to review the data. In addition, the DSMB Chair may request a meeting at any time.

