This marks the end of the 6-week study period. Clinical data (HbA1c) along with total daily insulin requirement and pump settings at the end of the study will be collected. Short questionnaire asking for feedback using the 780G pump with SmartGuard, will be given to parents (optional).

[figure not shown]
Wash-out period: There should be a minimum wash-out period of 3 months for participants willing to enrol for the larger RCT. The 3-month period is chosen to minimise the impact of any carry over of glycaemic impact with AHCL into the larger RCT.

Randomized Controlled Trial (RCT) Phase

This is a **prospective multicentre randomised controlled, two-arm unblinded, parallel study** in free-living conditions, in young children with type 1 diabetes on insulin pump therapy. Participants will be randomised in two groups; either the control group (standard therapy) or the intervention group (AHCL). The control group will be participants on continuous subcutaneous insulin infusion (CSII) with or without CGM (continuous glucose monitoring). The study duration is for 3 months. This phase will be conducted at four tertiary paediatric diabetes centres (Perth Children’s Hospital, WA, Westmead Children’s Hospital, NSW, Women’s and Children’s Hospital, SA, and Royal Children’s Hospital, VIC).

AHCL group: Investigational pump for 3 months OR Control group: Standard CSII for 3 months.

The study design is as shown in the Figure 2 as below.

*Visits 2B,2C, 5C, 5D optional if data requirement from blinded CGM not met, Visit 5 Blinded CGM only for control group.

Figure 2: Study design RCT

VISIT 1

(Eligibility Confirmation, Baseline data collection and commencement of run-in period).

Information sheets will be provided in advance to participants who potentially fit inclusion criteria. HbA1c should be available from last clinic visit within 3 months of Visit 1.

Participants will be checked if they meet the inclusion criteria listed below in Section 5.2. The following data will be recorded:

1. Consent signed by parent and investigator
2. Auxology
 - a. Height
 - b. Weight
 - c. BMI
3. Demographic
 - a. Date of Birth
 - b. Gender
4. Diabetes clinical
 - a. Date of diagnosis
 - b. Current pump/CGM therapy
 - c. HbA1c
 - d. History of severe hypoglycaemia – coma or convulsion or episodes requiring third party assistance (events in last 12 months).
 - e. History of diabetic ketoacidosis (DKA) in the last 12 months

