Visit 4D: Review of AHCL (after 4 weeks from commencement of AHCL, 1 hour)

Face-to-face meeting to upload insulin pump, review CareLink reports and revise settings (CHO ratio and Insulin action time)

Participants will be issued with enough consumables for the study.

Research staff will review CGM data at 8 weeks' with participants encouraged to contact the team if support/assistance required.

VISIT 5 (11 weeks after randomisation for control arm only)

Visit 5A: Insertion of blinded CGM: This constitutes first of the two sensors, each sensor provides data for 7 days. Parents will be instructed to test their children for a minimum 3 to 4x/day using the study meter.

Visit 5B: Insertion of 2nd blinded CGM: Participants will return 7 days after sensor insertion to remove and download the first week of CGM data. The study meter will be uploaded. A new sensor will be inserted and a fresh transmitter attached.

A total of 2 weeks of blinded sensor is required with at least 10 days of data. In participants who do not meet this requirement, repeat sensors will be offered till a maximum of 4 attempts of data collection

Visit 5C: Insertion of 3rd blinded sensor (if applicable)

Visit 5D Insertion of 4th blinded sensor (if applicable)

VISIT 6 (1 week after last blinded sensor) **End of RCT Phase**

The following data will be collected:

1. Auxological
 - a. Height
 - b. Weight
 - c. BMI
2. Diabetes clinical
 - a. HbA1c
 - b. Total daily dose of insulin (mean of previous 7 days)
 - c. Pump upload (for intervention group)
 - d. Severe hypoglycaemia since Visit 5 for Control arm / Visit 4d for Intervention arm
 - e. Diabetic ketoacidosis since Visit 5 for Control arm / Visit 4d for Intervention arm
 - f. Hospital admissions since Visit 5 for Control arm / Visit 4d for Intervention arm
3. Psychology measures: Psychological scales will be administered to parents on an electronic platform.
 - a. Functional health status: Quality of life (QOL) WHO 5, EQ5D
 - b. Fear of hypoglycaemia: Hypoglycaemia fear survey Parent
 - c. Diabetes-related distress: Problem Areas in Diabetes PAID-Parent version
 - d. Anxiety: GAD-7
 - e. Sleep quality: Pittsburgh Sleep Quality Index
 - f. Technology acceptance and satisfaction: DTQ
4. 24-hour food recall interview (to capture dietary pattern)
5. Parents of participants will be offered a semi-structured interview at the end of the study to share the lived experiences with use of new technology.

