5.4 Participant withdrawal criteria

(a) when and how to withdraw participants from the investigational product/study treatment;
The participant may withdraw from the study at any time. They can do so by contacting the research staff.

(b) the type and timing of the data to be collected for withdrawn participant(s);
As this is an intention-to-treat, the data for withdrawn participants will be used for analysis

(c) whether and how participants are to be replaced;
Participants will not be replaced.

(d) the follow-up for participants withdrawn from the investigational product/study treatment.
The participants will go back on their standard therapy and will be followed up as their regular clinic visits.

6 Treatment of Participants

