6.3 Monitoring of participant compliance

The study is targeted at young children primarily supervised by parents/caregivers and hence a high degree of engagement with the study is expected.

Participants using the AHCL device will receive support from the research staff to help them familiarise themselves with the AHCL system. As this cohort is already on insulin pump therapy with most of the children on sensors, adaptation of this technology is not expected to be challenging.

Parents will also receive assistance to help troubleshoot sensor issues. They will be able to upload the pump at home, review reports and this will provide an opportunity to engage and encourage the use of the system.

7 Assessment of Efficacy

The efficacy of the device will be assessed through the Randomised Controlled Trial. 7.1 Primary outcomes

The primary outcome is the percentage of time spent in target glucose range (3.9-10 mmol/L) measured at 5-minutely intervals by a blinded CGM over 2 weeks starting at 13 - 15 weeks post randomization. Percentage of time spent in target glucose range will be calculated by dividing the number of sensor readings falling in the range 3.9-10 mmol/L by the total number of sensor readings and multiplying by 100. Participants will be considered to have missing data if they have fewer than 10 days with 70% valid sensor readings.

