9.6 Data management

Data collected from each site will be stored in the respective study sites' secured servers, in accordance to data storage policies in each site. These data will all be entered, in a de-identified manner into a robust

data capture platform, REDCap, in which the forms were built and validated by a data manager based in Telethon Kids Institute.

All anonymised data will not be able to be linked back to any individual participant. Data will be stored on secure servers and electronic device capture systems with secure access for study staff only. All data will be stored at least for 25 years in line with GCP requirements on secure servers. Hard copies of participant notes will be stored in secure filing cabinets at each site and archived in secure facilities' at the end of the study.

All anonymised data will be risk rated at the completion of the study and stored in data repositories according to the Institution's data sharing policies and plan, and may be used for unspecified future research. Only published and permanently de-identified data will be deposited into publicly accessible repositories which will be safeguarded by Australian Data Archives (ADA) through a data sharing agreement with Telethon Kids Institute. The ADA main server is based in ANU and is a Core Trust Seal Certified repository.

Medtronic CareLink® System:

This system allows the study device to send information over the internet using a telecommunication network (such as a cellular network, wireless network, etc.). The information available from the Medtronic CareLink system is the same information the study team would collect from your device during an in-person office visit. Medtronic will receive participant's coded (deidentified) device data from CareLink®.

Medtronic takes steps to protect the privacy of the health information sent to the Medtronic CareLink Network over the internet. However, Medtronic cannot guarantee the health information is protected against unauthorised interception.

9.7 Procedures for missing, unused and spurious data:

Multiple imputations using multivariate normal regression imputation will be employed to account for missing/spurious data. Analysis using complete case and multiple imputation methods will be presented.

10 Monitoring / Audit

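### Children who stop AHCL may have no primary-outcome measurement, because the visit schedule and sections 4.9, 5.4(d) and 7.1 disagree on end-of-study CGM

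*Protocol*

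**What the plan says.** Section 4.9 lists criteria for discontinuing AHCL in a child. A child who stops and is willing to continue stays in the trial: "they will remain in the study and will continue to make all of the scheduled visits and participate in all monitoring". The same section states that the primary analysis is intention to treat.

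The RCT visit schedule in section 4.2 heads the end-of-study sensor visit "VISIT 5 (11 weeks after randomisation for control arm only)", and the Figure 2 footnote repeats the restriction: "Visit 5 Blinded CGM only for control group". At Visit 6 the only device data listed for the AHCL arm are "Pump upload (for intervention group)". Visit 6 counts events from Visit 5 in controls but from Visit 4D in the AHCL arm, which confirms that the AHCL arm has no Visit 5.

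Section 7.1 defines the primary outcome as time in range "measured at 5-minutely intervals by a blinded CGM over 2 weeks starting at 13 - 15 weeks post randomization", with no restriction by arm. It adds: "Participants will be considered to have missing data if they have fewer than 10 days with 70% valid sensor readings".

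Section 5.4(d), whose prompt covers withdrawal from the study treatment, says: "The participants will go back on their standard therapy and will be followed up as their regular clinic visits". Standard therapy is CSII with or without CGM (section 4.2).

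On missing outcomes, section 9.7 says: "Multiple imputations using multivariate normal regression imputation will be employed to account for missing/spurious data". Complete-case results are to be presented as well. The predictors in the imputation model are not stated.

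**The concern.** An intention-to-treat estimate needs the outcome of every randomised child, whether or not the device is still in use. A child can comply fully with section 4.9 and attend every visit scheduled for the AHCL arm, yet none of those visits places a blinded sensor. If the child has also left the study system, the pump upload supplies nothing for the outcome window.

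The gap affects one arm only. A control child who has the same clinical event carries on and is measured at Visit 5. The triggers for stopping in section 4.9 (severe hypoglycaemia, severe DKA, non-compliance or a new condition judged to raise risk) make it unlikely that stoppers are a random subset.

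At stake is whether the estimate reported as intention to treat includes these children's actual glucose control, or replaces it with values modelled mainly on children still using the device. A SAP can choose the imputation model, but it cannot recover sensor data that no visit collects.

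**Working it through.** **Passages side by side, for an AHCL-arm child who has stopped and left the study system**

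- 4.9: follow all scheduled visits and monitoring.
- Visit 5 and Figure 2 footnote: no blinded CGM in this arm.
- Visit 6: pump upload only, which a child off the study pump does not generate.
- 7.1: outcome by blinded CGM in every child, starting at weeks 13 to 15. No AHCL-arm visit carries this out, and the timing differs from the week 11 start of Visit 5.
- 5.4(d): regular clinic visits, which need not include any sensor.

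These cannot all be followed. Under the visit schedule the outcome may be missing; under 7.1 it should exist.

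**The plan's own figures (section 9.2)**

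Inputs: control mean 55%, SD 11.5, difference 8 points, two-sided alpha 0.05, 80% power.

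- Normal approximation: n = 2 × (1.96 + 0.84)² × (11.5/8)² ≈ 32.4, so 33 per group against the stated 31. At 31 per group, power is 78.2% (76.9% by the t test). The stated figure is reproduced approximately.
- Dropout: 31/0.9 = 34.4, so 35 per group and 70 in total, as stated.

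**Size of the possible overstatement**

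Let m be the share of the AHCL arm that stops and has no CGM, and r the fraction of the 8-point benefit these children lose. If they are measured, the effect is 8(1 − m·r). If they are imputed as on-device, it stays at about 8. The excess is 8·m·r. The protocol gives neither m nor r, so both are assumptions.

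| m | Effect if measured, r = 1 | Excess, r = 1 | Excess, r = 0.5 |
|---|---|---|---|
| 1 child in 35 | 7.77 | 0.23 | 0.11 |
| 5% | 7.6 | 0.4 | 0.2 |
| 10% | 7.2 | 0.8 | 0.4 |
| 20% | 6.4 | 1.6 | 0.8 |

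**Simulation check**

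Settings: 35 per arm, SD 11.5, assumed baseline correlation 0.5, stoppers chosen at random, all unmeasured and back at the control level; normal multiple imputation (20 imputations) followed by ANCOVA, 1,500 trials per setting. The imputation model held arm and baseline, with no stopping indicator and no post-stopping variable.

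| m | All randomised measured | Multiple imputation | Complete case |
|---|---|---|---|
| 5% | 7.61 | 8.00 | 8.00 |
| 10% | 7.18 | 7.98 | 7.98 |
| 20% | 6.39 | 8.00 | 8.00 |

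Imputation and complete case agree, so presenting both would not expose the problem. With arm left out of the imputation model, the estimates were 7.71, 7.62 and 7.01 against 7.52, 7.25 and 6.36, an excess of about 0.2, 0.4 and 0.7 points.

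**Scale**

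The unadjusted standard error is 11.5 × √(2/35) = 2.75 points. An excess of 0.8 is 0.8/2.75 ≈ 0.3 standard errors; one stopper's 0.23 is less than 0.1.

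**The case against.** Several points on the other side have weight.

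- **Section 7.1 calls for blinded CGM in all participants.** Read alone, it gives a stopper who stays in follow-up an outcome. This stands: a reader might infer that these outcomes are missing by design, but that requires Visit 5 to override 7.1, and nothing says it does. What can be shown is a contradiction, and 7.1 has no AHCL-arm visit that delivers it.
- **Stopping AHCL need not mean leaving the study system.** The protocol equates AHCL with SmartGuard, one of two modes of the 780G. Manual Mode also works with CGM, and section 8.2(d) uses it as an interim fallback. Section 6.3 says most of the children are on sensors already. Such data may exist; the protocol does not say whether they would count.
- **Sections 5.4(d) and 4.9 may address different children.** Section 5.4(a) describes families who choose to leave, and 4.9 describes stopping by criterion. Clinic visits do not exclude study visits. Even so, the prompt to 5.4(d) covers withdrawal from study treatment, so the overlap needs settling.
- **The imputation model is open.** A reader might infer that stoppers would certainly be imputed as if still on the device. The protocol does not say so. Visit 6 collects HbA1c in both arms, and using it would pull a stopper's imputed value towards that child's actual control. The predictors may be set in a SAP that is not shown.
- **Rate and direction are assumed.** The 10% in section 9.2 is total dropout across both arms, not stopping AHCL while remaining in the study. Severe hypoglycaemia does not by itself imply low time in range in the measured fortnight. The bias favours the device only if stoppers lose benefit, which is plausible after a return to standard therapy but not established.

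**Conclusion.** The concern holds as an inconsistency with a conditional consequence. Sections 4.9, 5.4(d), 7.1 and Visit 5 do not together secure a primary-outcome measurement for an AHCL-arm child who has left the study system, although the stated analysis needs one.

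The consequence depends on three things that the protocol leaves open: how many children stop, how much benefit they lose, and whether the imputation model represents stopping or uses post-stopping data. If it does neither and the full benefit is lost, the overstatement is about 0.23 points per stopper in 35, or 0.4 to 1.6 points of 8 at an assumed 5% to 20% stopping. It halves if half the benefit is lost. With few stoppers this is small against the standard error, but it acts in one direction and the planned complete-case analysis would not reveal it.

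The documents do not support the stronger conclusion that the trial will overstate the effect. They do support correcting the schedule, because the missing measurement cannot be recovered at the analysis stage.

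**What to change.** 1. Extend the end-of-study blinded CGM to any AHCL-arm participant no longer using the study system, in the same window and with the same data-sufficiency rule as the other participants.
2. Reconcile 4.9, 5.4(d), 7.1, Visit 5 and the Figure 2 footnote, so that stopping the device does not end outcome collection and the window is stated once (week 11 against weeks 13 to 15).
3. State whether sensor data from Manual Mode or from a child's own CGM can count towards the primary outcome.
4. Optionally, for stoppers who remain unmeasured, add a sensitivity analysis that imputes them from the control arm. This can sit in the SAP.

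Cost: two blinded sensors for each child who stops, and up to four if repeats are needed under the existing limit, with the associated sensor visits. At the assumed 5% to 20% of 35, that is about 2 to 7 children, or 4 to 28 sensors. The rest is wording and, if adopted, one further analysis. No change to the criteria for stopping the device is implied.

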8.2 Safety

This is a cohort of young children with T1D supervised by their parents/caregivers.

Participants will be contacted on a weekly basis (or more frequently as required) during the entire duration of the feasibility phase and for at least 4 weeks of the larger RCT after commencement of AHCL to review progress. During the feasibility phase, the research nurse will also follow the participant in real-time. Real-time glucose levels will also be available to the caregiver/parent at all times.

- a. Participants with high blood/sensor glucose levels will be advised to test for blood ketones.
- b. Participants with hypoglycaemia will be advised to take appropriate clinical action.
- c. Weekly review of time spent in hypoglycaemia range will be evaluated by the research doctor. Any instance of a week where percentage of time spent <3.9 mmol/l exceeds 8% and/or percentage of time <3 mmol/L exceeds 2 % will be recorded as an adverse event.
- d. Participants using the AHCL system will be informed to contact the research diabetes educator if they experience technical issues with the sensor and/or system and to revert to manual mode (standard pump) in the interim.
- e. Participants in the control group will be advised to follow the clinical pathway while participants in the intervention group will be advised to contact the research doctor/diabetes educator.
- f. In the event of device (pump) failure, the participant will be advised to switch to their standard pump therapy (own pump) and contact the research doctor/diabetes educator.
- g. Patients are educated regarding awareness of insulin infusion failure (rising blood glucose levels and ketones) and how to manage this (using standard injected subcutaneous insulin, and change insulin infusion set).
- h. Any admissions to hospital for DKA or severe hypoglycaemia will be reported to the principal investigator within 24hrs with notification to the lead site.
- i. Establishment of Data and Safety Monitoring Board (DSMB) to review progress

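### The enrolment pause and 7-day DSMB meeting for severe DKA depend on an algorithm attribution that the DSMB itself is asked to decide

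*Protocol*

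**What the plan says.** Protocol section 4.9 contains one study-level rule for a single DKA: "An instance of severe DKA from Automode use (algorithm-related) in the AHCL group will result in temporarily stopping additional enrolment of participants". The pause lasts until the DSMB has reviewed the data to "determine whether the event was triggered by the system or not and whether it is safe to proceed". The next sentence adds: "An emergency meeting of the DSMB will be convened within 7 days to review the data". No separate trigger is given for that meeting. The Chair may also ask for a meeting at any time.

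Other provisions that bear on a DKA:

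- Section 4.9, criteria for discontinuing AHCL in one child, lists "Severe diabetic ketoacidosis (venous ph <7.2)" with no reference to cause. Section 8.4 uses the same threshold to define a severe adverse event.
- Section 4.9, overall suspension: "In case of a recurring system malfunction or participant safety issue observed with multiple participants, the overall study will be suspended".
- Section 4.9, primary safety outcome: "As hypoglycaemia events are experienced during the study, the DSMB will be notified in real time".
- Section 8.2h: "Any admissions to hospital for DKA or severe hypoglycaemia will be reported to the principal investigator within 24hrs with notification to the lead site".
- Sections 8.3 and 10.2 give the DSMB accruing data and data access, and provide for monthly monitoring by the coordinating principal investigator.

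**The concern.** The rule takes as its entry condition something it then asks the DSMB to establish. If a site first ascribes a severe DKA in an AHCL child to infusion-set failure or illness, or has not yet settled the cause, the condition is not met on the words used and neither the pause nor the dated meeting follows. The investigator's first judgement then decides whether the independent body is convened.

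That first judgement can be uncertain on the protocol's own account. Section 8.1 says under-delivery by the system can lead through persistent high glucose and ketosis to ketoacidosis. Section 8.2g gives rising glucose and ketones as the signs of infusion failure. The early picture is therefore much the same for a system cause and a set failure. These are children from 2 years of age, on a device that the protocol's background section calls investigational.

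**Working it through.** The protocol gives no DKA rate and no attribution probability, so there is no stated figure to reproduce. The check is mainly a comparison of provisions.

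**1. What each provision does for a first severe DKA in an AHCL child whose cause is initially put elsewhere**

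| Provision | Needs algorithm attribution? | Reaches DSMB by a deadline? | Pauses enrolment? |
|---|---|---|---|
| 4.9 single-DKA rule | Yes | Yes, 7 days, once triggered | Yes, once triggered |
| 4.9 criterion for AHCL use in that child | No | No | No |
| 4.9 overall suspension | No, but needs recurrence or multiple participants | No | Study suspended, but not on one event |
| 4.9 real-time DSMB notice | Not applicable: written for hypoglycaemia | Not for DKA | No |
| 4.9 Chair's request | No | Discretionary, no deadline | No |
| 8.2h 24-hour report of admissions | No | Goes to principal investigator and lead site; DSMB not named | No |
| 8.4 severe adverse event | No | No | No |
| 8.3 and 10.2 data access and monitoring | No | No deadline for a single event | No |

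Only the first row gives an automatic pause and a dated independent review, and it alone has the causal condition.

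**2. Effect of the condition on a first event**

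Let q be the probability that a severe DKA in the AHCL group is initially called algorithm-related. On the literal wording, P(first event starts the pause) = q. With a cause-neutral trigger it is 1. The value of q is unknown. Over an assumed range:

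- q = 0.25: 1 − 0.25 = 75% of first events start neither step
- q = 0.50: 50%
- q = 0.90: 10%

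Some of these events would be correctly put down to another cause, so these are not rates of harm.

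**3. How often the question would arise**

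Section 9.2 plans 70 children, so about 35 on AHCL. Over 3 months, exposure is 35 × 0.25 = 8.75 child-years. Assume a severe DKA rate of 1, 2 or 5 per 100 child-years, and let m = rate × 8.75 be the expected number of events. P(at least one) = 1 − exp(−m), and P(two or more) = 1 − exp(−m)(1 + m).

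| Assumed rate per 100 child-years | m | At least one | Two or more |
|---|---|---|---|
| 1 | 0.0875 | 8.4% | 0.4% |
| 2 | 0.175 | 16.1% | 1.4% |
| 5 | 0.4375 | 35.4% | 7.2% |

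At these rates a first event would usually be the only one, so a suspension rule that needs recurrence or several participants would seldom stand in for the single-event rule.

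Multiplying the extremes, the chance that a first event occurs and starts neither step runs from 8.4% × 0.10 = 0.8% to 35.4% × 0.75 = 27%. That range follows from the assumptions and is too wide to serve as an estimate.

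**4. Cost of a cause-neutral trigger**

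The chance of any pause in the RCT is at most the at-least-one column, 8% to 35%, because an event after enrolment closes pauses nothing. Section 4.8 gives 24 months for recruitment, visits and analysis together. If recruitment takes 12 to 18 of those months (an assumption), the rate is 70/12 = 5.83 to 70/18 = 3.89 children a month. A 7-day pause then defers 5.83 × 7/30.44 = 1.3 to 3.89 × 7/30.44 = 0.9 enrolments, about one.

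**The case against.** The best reply is that the sentence should be read whole. If the cause had to be settled before entry, the DSMB's first question would have nothing left to decide, so the authors probably meant a suspected event. As a statement of intent that is likely right. But the word suspected is absent, and the parenthesis in the trigger points the other way. A site deciding quickly should not have to infer the rule.

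A second reply is that confining a study-wide pause to device-related DKA is defensible. All participants already use pumps, infusion failure can occur on any pump, and the stored sensor and insulin data inform the first call. This stands in part. The same data would be available to the DSMB, though, and at the assumed rates the cost of letting it decide is small. A DSMB charter or the planned manual of operations may also name who makes the first attribution. For that reason the point does not rest on nobody being named.

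A reader might infer two stronger conclusions. One is that a misattributed severe DKA would escape oversight. The documents do not support this: section 8.4 classes it as a severe adverse event whatever its cause, section 8.2h sends any admission to the principal investigator and lead site within 24 hours, section 4.9 makes it a criterion for discontinuing AHCL in that child, and the DSMB has data access and a Chair who can convene it. The other is that a definite number of further children would be enrolled meanwhile, for example until the monthly monitoring in section 10.2. That fails as well. The investigators already know within 24 hours, and nothing in the protocol links a pause or a re-attribution to the monthly check.

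**Conclusion.** The point holds as a minor defect of wording with a safety purpose. Taken literally, section 4.9 lets the first attribution decide whether the automatic pause and the 7-day DSMB meeting happen, although attribution is a matter for that meeting, and section 8.2h does not bring the DSMB in by another route. What is missing is automatic independent review of a first event not labelled algorithm-related. Awareness of the event is not missing. The conclusion rests on comparing the provisions and needs no assumed rate. The percentages in the working only illustrate how often the rule might be tested, and no count of extra enrolments can be derived from the protocol. This is a cheap improvement.

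**What to change.** In section 4.9, let any severe DKA (venous pH below 7.2, the threshold already in sections 4.9 and 8.4) in a child using AHCL pause enrolment and convene the DSMB within 7 days, whatever the presumed cause. At the least, write suspected or possible system contribution. State that the DSMB or its Chair decides attribution and any early lifting of the pause. An exemption applied by the site for events it regards as clearly unrelated would keep the same gate in place. In section 8.2h, copy the DSMB Chair on the 24-hour DKA report.

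The change is one clause in 4.9 and one addition in 8.2h. Its downside is an occasional short pause and a DSMB review for an event that proves unrelated. The Chair's power to lift the pause early would shorten it further.
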